As with motivational interviewing, many brief interventions have incorporated specific CBT techniques into their protocols. One commonly used technique (drawn from CBT-based relapse prevention) is mindfulness. Mindfulness is a state of awareness in which individuals are focused on, and accepting of, the present moment (Creswell, 2017). Specific mindfulness exercises (e.g., body scans, focusing on breathing, paying attention to sensory experiences) can be used to foster awareness and acceptance of one’s thoughts, feelings, and sensations. Notably, mindfulness

has been used as an effective coping strategy for craving (Schmidt, Lumley, & Grekin, 2023; Witkiewitz, Marlatt, & Walker, 2005), particularly among individuals who drink to cope with negative affect (Wisener & Khoury, 2021).

Another commonly used CBT technique is education about protective behavioral strategies (PBS). Protective behavioral strategies are self-regulated behaviors that can minimize the consequences and harm associated with alcohol consumption (e.g., consuming water between drinks of alcohol, picking a designated driver, avoiding drinking games, etc.; Martin et al., 2020). Evidence suggests that the use of PBS is associated with reduced drinking and fewer alcohol-related consequences within both young adult and adult samples (Benton et al, 2004; Ray et al., 2009). Additionally, studies show that the relationship between binge-drinking and alcohol-related problems is weaker among young adults, who report more frequent use of PBS (Borden et al., 2011).

Brief Alcohol Interventions: Efficacy and Dissemination Issues

Although brief interventions are widely used and grounded in empirically-supported therapies, their effects have nonetheless been modest, with meta-analyses yielding effect sizes in the small to moderate range, and many individual efficacy trials producing null results (Butler et al., 2013; Kaner et al., 2013; Maio et al., 2005). Studies focusing specifically on brief interventions for young adults and college students have produced similar findings. In fact, three recent meta-analyses suggest that the effects of brief interventions for young adult drinkers are non-significant (Huh et al, 2015) or very small (Carey et al, 2007; Foxcroft et al, 2014).

Brief alcohol interventions have also been negatively affected by implementation challenges. Specifically, health care providers with limited time and training are often unable or

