In light of these data, the aim of the current study is to test the efficacy of a fully online, Instagram-based intervention designed to reduce heavy alcohol use among young adults. Participants will be randomly assigned to either an intervention or an assessment-only control condition. Analyses will compare mean changes in past-month alcohol use, alcohol-related consequences, mindfulness, and use protective behavioral strategies in intervention versus control group participants at 10-week follow-up. Secondary analyses will assess the perceived acceptability of the intervention and its posts, as well as the degree to which the posts were seen and remembered by participants. It is hypothesized that (1) participants in the intervention group will show greater decreases in alcohol use and consequences and greater increases in mindfulness and protective behavioral strategy use than participants in the control group and (2) intervention posts will be remembered and given high acceptability ratings.

Pilot Work

The proposed project will build on a pilot study conducted by the PI between April 2021 and December 2021. During this pilot study, 50 Wayne State University students between the ages of 18-28, who reported regular binge drinking, were given an Instagram-based alcohol intervention (developed specifically for the study by the PI). After an initial orientation session, participants were asked to follow the study Instagram page and were then shown intervention posts each day for 6 weeks. A subset of participants was also exposed to a series of Instagram ‘stories’

(i.e., images that are available for viewing for twenty-four hours after posting), which were posted once every two days. Instagram content consisted of mindfulness exercises, presentation of drinking norms, information about protective behavioral strategies, and specific affirmations (described in more detail below).

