The intervention was rated as highly acceptable. Additionally, analyses revealed significant within-subjects decreases in past-month alcohol consumption, drinking days, and binge-drinking days post-intervention; however, there were no significant changes in past-month protective behavioral strategies and mindfulness practices. Although this pilot study provided critical feedback about intervention development and administration, it was intentionally small and did not include a control group, thereby limiting the interpretation of findings. The proposed study builds on this pilot work by replicating the study with a larger sample size, a community-based sample, and an assessment-only control group. Specific procedures are described below.

Chapter 2: Methods

Participants

Eighty participants will be recruited from Prolific, an online platform designed to screen and recruit potential research participants for online studies. Power analyses indicate that, with an N of 80 (two groups of 40), this study will be sufficiently powered to detect effect sizes of .20, an effect size consistent with other standalone, technology-delivered, cognitive behavioral interventions for alcohol use (Kiluk et al., 2019).

In order to be eligible for the study, participants must: (1) be a US resident, (2) be between the ages of 18 and 30; (3) report at least two binge-drinking episodes (i.e., four or more drinks in one sitting for cis women, five or more drinks in one sitting for cis men or transgender and

nonbinary individuals) per month over the past three months; (4) have an active Instagram page; and (5) report regular Instagram use (i.e., at least 2-3 times a week).

Participants will be randomized to either an intervention condition in which they will follow an Instagram page and engage with content during the six-week study period or to an assessment-only control condition in which they will be emailed assessment measures, but will not be exposed to intervention content.

Measures

Demographics will be assessed at baseline. Participants will be asked to answer questions about their sex, gender, age, race, ethnicity, sexual orientation, education level, and household income. State of residence will also be assessed.

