In order to prevent delays between baseline survey completion and the start of the Instagram intervention, subgroups of participants may be randomized to condition and exposed to the intervention in different data collection waves. Each wave will last for six weeks and will contain a total of forty-two Instagram posts and twenty-one Instagram ‘stories’ (i.e., images that are available for viewing for twenty-four hours after posting and can utilize mechanics like polls and quizzes). Intervention content will be posted once per day throughout the 6-week intervention period, alternating between posting times of approximately 8 AM EST/EDT and 8 PM EST/EDT, and intervention ‘stories’ will be posted once every two days.

10-Week Follow-Up Survey. Ten weeks after the intervention start date (and four weeks after the end of the intervention), participants will be emailed a follow-up survey, which will contain the same questionnaires as the baseline survey. Participants in the intervention condition will also be asked to rate how relevant, respectful, helpful, empathic, personalized, and interesting they felt the intervention content had been, using 5-point Likert scales. Additionally, participants in the intervention group will be shown specific examples of previously posted content and asked to rate each specific post on the dimensions listed above, as well as to indicate whether they remembered seeing those particular posts.

The follow-up survey will remain open for two weeks, and reminder messages will be sent during this time to encourage participant completion. Each participant will receive \$10 for completing the baseline session and \$15 for completing the 10-week online follow-up survey.

Analytic Strategy and Hypotheses

The data will be assessed for normality, missing data, and outliers. Data transformation, multiple imputation, and list-wise deletion will be utilized as needed. Mixed repeated-measure ANOVAs will be used to analyze within- and between-group differences in participants' alcohol consumption, alcohol-related consequences, mindfulness practices, and use of protective behavioral strategies at baseline and 10-week follow-up. Average acceptability ratings will be calculated using group means.

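### The power statement gives no metric for its effect size of .20: as a standardised mean difference, 40 per arm give about 14% power; as interaction f, power is adequate but for a 0.80 SD effect

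*Combined protocol and SAP*

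**What the plan says.** The only sample-size justification is in Chapter 2: Methods, Participants. It says that "with an N of 80 (two groups of 40), this study will be sufficiently powered to detect effect sizes of .20" and describes .20 as "an effect size consistent with other standalone, technology-delivered, cognitive behavioral interventions for alcohol use", citing a paper that the reference list identifies as a meta-analysis. The same .20 is therefore both the effect the trial can detect and the effect to be expected from similar interventions.

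The planned test is in Analytic Strategy and Hypotheses: "Mixed repeated-measure ANOVAs will be used to analyze within- and between-group differences" at baseline and 10 weeks. The aim, at the end of the Instagram Interventions section, sets the contrast: "Analyses will compare mean changes in past-month alcohol use" and the other outcomes between the two groups.

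Recruitment equals the number in the power statement ("Eighty participants will be recruited from Prolific"). For incomplete follow-up, the procedure says that "reminder messages will be sent during this time to encourage participant completion", and the analysis section says that "multiple imputation, and list-wise deletion will be utilized as needed". No dropout rate or allowance is given. Nowhere do the documents state the metric of .20, alpha, sidedness, target power, the assumed correlation, or the outcome for which power was computed.

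**The concern.** A treatment effect benchmarked against other trials is commonly expressed as a standardised mean difference. On that scale .20 is small, and 40 per arm is far too few to detect it reliably. Yet .20 could also be Cohen's f, a usual input when power is computed for a mixed ANOVA. In this two-group, two-time design, f of .20 for the interaction is a much larger effect.

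The sentence needs both of its parts to hold on one scale: the trial can detect .20, and .20 is what similar interventions achieve. If the scales differ, a reader will believe that the trial can find the effect expected of its class when it may be powered only for one four times as large. That affects how the efficacy aim is judged and how the result is read.

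**Working it through.** **Inputs from the documents.** 40 per arm; effect size .20, metric not given; one baseline and one follow-up; group-by-time comparison.

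**Assumed, because not stated.** Two-sided alpha .05; 80% as the minimum target power; no loss; equal SD at both times, set to 1; correlation ρ between baseline and follow-up varied.

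**Reproducing the plan's figure.** This cannot be done from its own inputs. If .20 is interaction f and ρ = .5, a total of 52, 68 or 84 gives 80%, 90% or 95% power. None of these is 80, although 80 exceeds the first two.

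**Test.** In a 2×2 mixed ANOVA the group-by-time test is a two-sample t test on change scores with 78 df. The SD of change is √(2(1−ρ)). For a difference in change of d (in raw SD), the noncentrality is d / √((2/40) × 2(1−ρ)).

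**Reading A: standardised mean difference, d = .20.** At ρ = .5 the standard error is √(0.05 × 1) = 0.224 and the noncentrality is 0.20 / 0.224 = 0.894, giving power of 14.3%.

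| ρ | 0 | .3 | .5 | .7 | .8 | .9 | .95 |
|---|---|---|---|---|---|---|---|
| Power | 9.6% | 11.6% | 14.3% | 20.7% | 28.7% | 50.6% | 79.8% |

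Other analysis choices do not rescue this reading. Adjusting for baseline instead (SD √(1−ρ²)) gives 17.5% at ρ = .5. One-sided alpha .05 gives 22.4% at .5 and 40.4% at .8. A simulation of 20,000 trials gave 14.8% at .5 and 28.3% at .8.

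**Reading B: Cohen's f = .20 for the interaction, with the correlation in the noncentrality.** λ = f² × N × 2 / (1−ρ) = 0.04 × 80 × 2 / (1−ρ) = 6.4 / (1−ρ). At ρ = .5, λ = 12.8.

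| ρ | 0 | .2 | .3 | .5 | .7 |
|---|---|---|---|---|---|
| Power | 70.5% | 79.8% | 84.8% | 94.2% | 99.5% |

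In this layout f = d/4, so f = .20 is d = 4 × 0.20 = 0.80 raw SD at any ρ. The two readings differ fourfold (0.80 / 0.20).

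**Other readings.**
- Plain between-group f = .20 (d = 0.40): 42% at ρ = .5, about 80% at .8.
- r = .20 (d = 2r/√(1−r²) = 0.41): 44% at .5, 81% at .8.
- f taken from partial eta-squared of the change (λ = 0.04 × 80 = 3.2): 42% at any ρ.
- f² = .20 (λ = 16): 98%. Eta-squared = .20 (λ = 20): 99%. These are differences of 0.89 and 1.00 SD of change.

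**Detectable difference.** With 40 per arm, 80% power needs 0.634 SD of change. Multiplying by √(2(1−ρ)) converts this to raw SD; at ρ = .7, 0.634 × 0.775 = 0.49.

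| ρ | 0 | .3 | .5 | .7 | .8 |
|---|---|---|---|---|---|
| Raw SD | 0.90 | 0.75 | 0.63 | 0.49 | 0.40 |

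**Sensitivity to loss.** If 20% were lost and not recovered by imputation (an assumption; 32 per arm), the detectable difference would be 0.71 SD at ρ = .5 and 0.55 SD at .7. Reading A would have 12% power at .5. Reading B would have 70% at .2 and 88% at .5.

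**The case against.** The best defence is that the authors meant interaction f. The planned analysis is a mixed ANOVA, f is a usual power input for it, and on that reading 80 participants are enough once the correlation is slightly above .2. This stands. No arithmetic error is proved, and a reader who infers that the trial is underpowered whatever .20 means would go beyond the documents. The mean-difference reading rests on the benchmark to a meta-analysis whose metric cannot be seen here.

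Three further inferences are tempting and unsupported.

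- That a 0.80 SD effect is refuted by the background section on brief interventions, which reports "meta-analyses yielding effect sizes in the small to moderate range" and smaller effects in young adults. That section gives no figures and covers brief interventions generally, not the class used as the benchmark. It suggests tension and no more.
- That the plan treats a non-significant result as excluding 0.20 SD. It says no such thing, and whether the data could exclude that effect depends on the correlation.
- That the plan contradicts itself on dropout. It gives no rate, and reminders and imputation are mitigation. The missing allowance is an omission.

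The defence does not settle the benchmark. If f was meant, the comparison with similar interventions has to be on the f scale too, and the text does not show that it is.

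**Conclusion.** The concern holds conditionally. As written, the power claim cannot be verified. If .20 is a standardised mean difference, the claim is wrong: power is 10% to 29% over correlations 0 to .8, and about 80% only near .95. If .20 is interaction f, the detection claim is right at correlations slightly above .2, but for a 0.80 SD difference in change, and the comparison with other interventions then lacks a shown basis. The figures assume two-sided alpha .05, no loss and equal SDs. The failure on the mean-difference reading does not depend on choosing correlation .5. Because this sentence is the only support for the sample size and uses one number for two purposes, this is more than a missing detail. Which metric was meant, and so whether the claim is false, remains open.

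**What to change.** Change the wording only; no participants or procedures are added.

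1. State the effect-size metric, the test, alpha and sidedness, target power and the assumed correlation.
2. Check the metric of the cited meta-analysis.
3. Restate the claim as a detectable difference in SD units. For example: *With 40 per arm and two-sided alpha [.05], the group-by-time test has 80% power for a difference in change of about 0.63 SD at correlation [.5], or 0.49 SD at [.7].* Bracketed values are assumptions for the authors to replace.
4. If a standardised mean difference was meant, this replaces the present detection claim. If interaction f was meant, label it as f = .20, a 0.80 SD difference in change, with at least 80% power at correlations slightly above .2. Keep the comparison with other interventions only if the source reports that metric.
5. Show loss to follow-up as a labelled sensitivity case, for example 0.71 SD at correlation [.5] if [20%] are lost.

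The cost is retrieving the settings of the power analysis and checking one source. The downside is that, if a mean difference was meant, the stated power becomes less favourable.

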Past Month Alcohol Use will be assessed with The Timeline Follow-Back (TLFB; Sobell & Sobell, 1996), a highly reliable interview that uses a calendar and multiple procedures to aid in the retrospective reporting of substance use. During the TLFB, participants are asked to report how many standard drinks they consumed each day, during the past 30 days. Before beginning the task, participants will be provided with a graphic that illustrates the size of a standard drink (Figure 1), as well as a calendar marked with major holidays (Figure 2). The online version of the TLFB has been found to be a reliable measure of alcohol use in young adult samples (Rueger et al., 2012).

Past-Month Alcohol Consequences will be assessed using the Brief Young Adult Alcohol Consequences Questionnaire (BYAACQ; Kahler et al., 2005), a well-validated 24-item questionnaire designed to assess high- and low-level drinking consequences commonly experienced by young adults. The BYAACQ has shown good validity among young adults and is

designed to be sensitive enough to detect drinking consequences within non-clinical samples (Stamates, Yang, & Lau-Barraco, 2022).

Protective Drinking Practices will be assessed with the Protective Drinking Practices Scale (PBS; Martin et al., 2020), a 20-item questionnaire which measures the frequency of protective behavioral strategy use in the past month (e.g., “Limited cash before going out” rated on a Likert scale ranging from ‘Never’ to ‘Always’). This measure has shown good validity for use among young adults in the United States (Jordan et al., 2021).

Mindfulness Practices will be assessed using the Mindful Attention Awareness Scale (MAAS; Brown & Ryan, 2003). The MAAS is a 15-item questionnaire that assesses the frequency of engaging in mindfulness and mindfulness-related practices (e.g., “I find it difficult to stay focused on what’s happening in the present” rated on a Likert scale ranging from ‘Almost Always’ to ‘Almost Never’). The MAAS has been well-validated in young adult populations (MacKillop & Anderson, 2007).

Intervention Acceptability will be assessed using six domains of acceptability (i.e., relevant, respectful, helpful, empathic, personalized, and interesting). A selection of individual posts will be rated, in addition to the overall intervention. Ratings will be made using single-item, 5-point Likert scales.

Intervention Content

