Each intervention post will contain at least one of five elements: mindfulness exercises, norm referencing, readiness assessment, affirmations, or protective behavioral strategies.

Mindfulness Exercises. Mindfulness posts in the current Instagram intervention consist of breathing and imaginal exercises that encourage participants to be attuned to the present moment.

Examples include statements such as, “Ever zone out while doing something boring? Next time, try focusing on your breathing” or “Give yourself a moment this morning to really taste whatever your morning drink is, whether it be coffee, tea, or water. Let yourself savor it. Notice the smell (if there is one), the temperature, the texture.” Given that there is a particularly strong relationship between acting with awareness (one specific facet of mindfulness) and reductions in alcohol consumption (Karyadi & Cyders, 2015), the mindfulness posts in the current study will aim to promote “acting with awareness” with regards to both alcohol use and everyday living.

Norm Referencing. Norm referencing posts in the current study will provide participants with information about binge drinking and its risks (e.g., “Binge-drinking is defined as: 4+ drinks in one sitting for women, 5+ drinks in one sitting for men”). Other norm referencing posts will use population statistics to prompt participants to consider how their drinking habits align with those of others their age (e.g., “In 2018, 63% of 18- to 24-year-olds reported no binge-drinking during the past month. Do you drink more than the average of people your age?”).

Readiness Assessments. Readiness assessment posts will use a readiness ruler to ask participants (1) how ready or able they are to reduce their alcohol use and (2) why they think they might be ready/able (e.g., “On a scale of 1 to 10, how confident are you that you could cut back on your drinking? Was your answer a zero? If it was another number, why is that? What makes you feel like you’re - even a little bit -ready to change your drinking habits? Think about strengths and past successes that you could draw on.”).

Affirmations. Affirmation posts will present participants with positive, encouraging statements that are generic enough to apply to many, but meaningful enough to tap into specific values. An example of an affirmation post is the sentence, “No one knows you better than you do!” Other affirmation posts will reference common values and skills (e.g., “You have the power to

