We predict that (1) intervention participants will show greater decreases than control group participants in past-month quantity and frequency of alcohol use, binge-drinking episodes, and alcohol-related consequences, and (2) intervention participants will show greater increases than control group participants in the use of protective behavioral strategies and mindfulness practices. We also predict that the intervention as a whole, and specific intervention posts will be remembered and rated as highly acceptable across several dimensions (i.e., relevant, respectful, helpful, empathic, personalized, and interesting).

Figures

Figure 1. Standardized Drink Infographic

Figure 2. Example of TLFB Calendar

**12 fl oz of
regular beer**

=

**8–9 fl oz of
malt liquor
(shown in a
12 oz glass)**

about 5%
alcohol

about 7%
alcohol

**5 fl oz of
table wine**

=

about 12%
alcohol

**1.5 fl oz shot of
80-proof spirits
(whiskey, gin, rum,
vodka, tequila, etc.)**

about 40%
alcohol

The percent of “pure” alcohol, expressed here as alcohol by volume (alc/vol), varies by beverage.

December 2022

Sunday	Monday	Tuesday	Wednesday	Thursday	Friday	Saturday
				1	2	3
4	5	6	7	8	9	10
11	12	13	14	15	16	17
18 Hanukkah Begins	19	20	21 Winter Solstice	22	23	24 Christmas Eve
25 Christmas Day	26 Hanukkah Ends / Boxing Day	27	28	29	30	31

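### The mindfulness outcome is labelled as practice, but what the plan shows of the scale points to attention, and no listed measure records doing an exercise

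*Combined protocol and SAP*

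**What the plan says.** In the combined protocol and SAP, Chapter 2, Measures: "Mindfulness Practices will be assessed using the Mindful Attention Awareness Scale" (MAAS). The next sentence describes the instrument: "The MAAS is a 15-item questionnaire that assesses the frequency of engaging in mindfulness and mindfulness-related practices". One of the 15 items is given as an example. It begins "I find it difficult to stay focused on", refers to the present moment, and is rated from almost always to almost never.

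Analytic Strategy and Hypotheses lists mindfulness practices among the outcomes for the mixed repeated-measures ANOVA and predicts that "intervention participants will show greater increases than control group participants in the use of protective behavioral strategies and mindfulness practices". The aims paragraph, just before Pilot Work, puts the same expectation differently: "greater increases in mindfulness and protective behavioral strategy use than participants in the control group". It does not mention mindfulness practices.

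Under Intervention Content, the mindfulness posts "consist of breathing and imaginal exercises that encourage participants to be attuned to the present moment". The same paragraph says their aim is to promote acting with awareness, both in drinking and in everyday life.

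**The concern.** Doing an exercise and being attentive are different things. By the sample item, a participant who did the posted breathing or mindful-eating exercise every day but remained distractible would be rated unfavourably. An attentive participant who ignored every post would be rated favourably.

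If the result is reported under the label the plan gives it, a difference between arms would read as more mindfulness practice, and a null as no effect on practice. Neither follows from an attention score. A null would also leave two explanations open: the exercises were not done, or they were done without a gain in attention.

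**Working it through.** The plan gives no figure to reproduce for this point, and it does not depend on sample size, alpha or power. The check is a comparison of the relevant sections, plus one calculation on recall windows.

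**1. Label against content.** The label and description in Measures, and the outcome name and prediction in Analytic Strategy and Hypotheses, all refer to practices. The one item shown names no activity; it rates a lapse of attention. The scale's title also refers to attention and awareness.

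**2. The plan's own distinction.** The background section on cognitive behavioral therapy defines mindfulness as a state of awareness and presents body scans, breathing and similar exercises as ways to foster it. Intervention Content follows the same logic: the posts are exercises and awareness is the goal. Exercise is the means and awareness the result. Labelling a score for the result as practice merges the two.

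**3. The neighbouring scale.** The protective-strategies scale, in the same section, asks how often concrete behaviours were used in the past month. The mindfulness entry shows no behaviour and states no recall window. Yet the prediction pairs them, expecting greater increases "in the use of protective behavioral strategies and mindfulness practices".

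**4. Other sources of data on practice.**

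| Planned data | What they record |
|---|---|
| Likes on posts | the post was seen |
| Recall of selected posts (intervention arm, follow-up) | the post was remembered |
| Acceptability ratings (intervention arm, follow-up) | opinion of the content |
| Timeline Follow-Back, consequences scale, protective-strategies scale | drinking, its consequences, protective behaviours |

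None records doing a mindfulness exercise, although the appendix posts and stories ask for specific ones, such as mindful eating, paced breathing and a mindful walk.

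**5. What a past-30-day item at follow-up would cover.** Posting runs for 6 weeks (6 × 7 = 42 days). Follow-up opens 10 weeks after the start (10 × 7 = 70 days) and stays open 2 weeks, to day 70 + 14 = 84.

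- Answered on day 70: the window starts at day 70 − 30 = 40, so about 42 − 40 = 2 of 30 days overlap posting.
- Answered on day 84: the window starts at day 84 − 30 = 54, so there is no overlap.

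Such an item would measure practice after posting ended, over the same window length as the Timeline Follow-Back. It could not show uptake during the intervention.

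**The case against.** The strongest reply is that the instrument suits the trial and only the label is loose. The aims paragraph says mindfulness, the posts target acting with awareness, and the scale appears to measure something close to that. This stands. A reader might infer that the wrong scale was chosen; the documents do not support that.

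Second, one item of 15 is shown. A reader might conclude that the whole scale rates everyday inattention, or that the trial can say nothing at all about practice. Both go too far: the content of the other 14 items is not in the documents, and the protocol's own description of the scale points the other way. What can be said is that the plan demonstrates no basis for a conclusion about practice.

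Third, Pilot Work reports that "there were no significant changes in past-month protective behavioral strategies and mindfulness practices", and it is tempting to attribute that null to the same mismatch. The pilot's mindfulness instrument is not named, so the inference fails.

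Fourth, measuring uptake is not a stated aim, and norm referencing, readiness assessment and affirmations have no matching outcome measure either. This is correct, and a missing uptake measure would not be a fault on that ground alone. Mindfulness differs because the plan makes a prediction about practices and so needs a measure of them.

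Finally, a report could simply present MAAS scores, so misreporting is not certain. That is true, but the label, description and prediction as written all lead towards the practice reading.

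**Conclusion.** The point holds as a mismatch between label and measure. Measures and Analytic Strategy and Hypotheses name, analyse and predict mindfulness practices, while the evidence shown about the scale indicates attention or awareness and no other listed measure captures practice. A between-arm MAAS difference should not be reported as a change in practice, and a null should not be read as exercises left undone.

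Its reach is limited: one of four outcome domains (alcohol use, consequences, mindfulness, protective strategies), and one of the two outcomes in the second prediction under Analytic Strategy and Hypotheses. The alcohol, consequences and protective-strategy results are unaffected. It should be corrected, but it does not threaten the trial's main question.

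The conclusion rests on reading the sample item and the scale's name as representative of the scale, and on the list of measures in the plan being complete.

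**What to change.** **Wording.** In Measures and in Analytic Strategy and Hypotheses, rename the outcome mindful attention/awareness. Correct the description of the scale, and state its scoring direction and recall window, since the item shown is negatively worded and no window is given. Restate the prediction as a greater increase in mindful attention. The aims paragraph needs no change. This costs only editing time.

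**If a practice hypothesis is kept.** Add one item in both arms, at baseline and week 10: on how many of the past 30 days was a mindfulness exercise done (for example focused breathing, mindful eating or walking)? Base any statement about practice on this item and report it as exploratory. Describe the week-10 answer as practice in about the month after posting ended.

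**If uptake during the intervention is of interest.** Add a separate question, in the intervention arm only, about the six-week posting period.

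The cost is one or two short self-report items, neither validated. If none is added, the wording change alone still prevents the unsupported conclusion.
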